### 8.1.3 Secondary Endpoints (immunological):

These endpoints will be measured using 4 blood samples collected pre-intervention in the emergency department, post-intervention in the emergency department, and at days 15 and 30 (as outpatients). At days 15 and 30, subjects will return to a clinic, phlebotomy site, or have outpatient phlebotomy to measure circulating antibodies. Each site will need to determine a blood sampling site that is qualified and safe for phlebotomy in persons with recent COVID-19 illness according to current CDC guidance. While guidance continues to evolve, patients are thought to be safe to leave isolation when symptoms have resolved for 3 days or at least 10 days have passed since COVID-19 diagnosis (<https://www.cdc.gov/coronavirus/2019-ncov/if-you-are-sick/steps-when-sick.html>), which will be prior to any of the in-person evaluations.

No more than 50 mL of blood will be drawn per day: 15 ml (one tablespoon) of whole blood will be collected from subjects at the following timepoints:

- After consent but before the administration of study intervention
- 1 (+/- 30 minutes) hours following the end of the administration of study intervention, and
- During study visits occurring on study days 15 and 30.

Whole blood will be processed into serum and plasma, and stored in a -70°C freezer or colder within 2 hours of sample collection. Samples will be shipped periodically to the study biorepository housed at the University of Pittsburgh.

Our exploratory aim is to characterize the agreement between or differences between the multiple assays for antibodies. This is important to inform future investigations about how to interpret titers reported by one platform or another. This will also inform about the development of innate immunity in control subjects. Increase in antibodies over time in CP recipients, if it occurs, will also inform about development of innate immunity after passive immunization. Therefore, we plan to perform multiple assays on any available sample from the donor unit, and also on the blood obtained from recipients of the intervention. Specifically, we plan to measure at least the following well characterized tests:

- Quantitate Anti-spike (S1) protein IgG, IgA titers (e.g. EUROIMMUN) on CP units
- Correlation of ELISA titers with Vitalant RVPN titers (neutralizing antibodies) on CP units
- Assessment of S1 titers in CP recipients and controls pre-CP, 1 hr post, 15 and 30 days post to assess the impact of CP and determine whether titers rise with time (showing endogenous response not negatively impacted by CP)
- Use Lentiviral pseudovirus reporter assay to quantitate neutralization Ab titers in recipients of CP units at pre- post-CP.
- Neutralization of SARS CoV-2 Plaque Formation (gold standard) in a subset of CP to correlate with other assays.

In addition to the blood samples collection outlined above, for subjects who consent to participating in an optional study evaluating the evolution of the adaptive immune response in CP recipients, an additional 20 ml of whole blood will be collected on the day of enrollment and

on study days 15 and 30. These samples will be shipped within 1 day of collection to a central laboratory for processing.

Residual viral media and saliva specimens collected will be analyzed for SARS-CoV-2 viral genotype

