For passive antibody therapy to be effective, a sufficient amount of antibody must be administered. When given to a susceptible person, this antibody will circulate in the blood, distribute into the total interstitial fluid in order to reach tissues, and provide protection against infection. As a rough estimate, one unit of donor CP (~250 ml) will be diluted into ~15 L of total extracellular fluid in an adult recipient, resulting in about 60-fold dilution of antibody concentration. For this reason, it is recommended that CP contain at least 1:80 titer and preferred 1:160 titer of antibodies against the pathogenic agent\*. Depending on the antibody amount and composition, the protection conferred by the transferred immunoglobulin can last from weeks to months.

\*<https://www.fda.gov/vaccines-blood-biologics/investigational-new-drug-ind-or-device-exemption-ide-process-cber/recommendations-investigational-covid-19-convalescent-plasma>

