## 2.3 Risk/Benefit Assessment

### 2.3.1 Known potential risks

A theoretical risk of CP is antibody-dependent enhancement (ADE) of illness. ADE involves an enhancement of disease in the presence of cross-reacting antibodies that activate receptors that suppress immune response. For coronaviruses, there is the theoretical concern that antibodies to one type of coronavirus could enhance infection to another viral strain. However, use of CP in the COVID-19 epidemic will rely on products with neutralizing antibody against the same virus, SARS-CoV-2, which should make ADE unlikely. The available evidence from the use of CP in patients with SARS1 and MERS and anecdotal evidence of its use in patients with COVID-19 ([http://www.xinhuanet.com/english/2020-02/28/c\\_138828177.htm](http://www.xinhuanet.com/english/2020-02/28/c_138828177.htm)) and, suggest it is safe. Nevertheless, this trial will monitor illness severity over time for any evidence of enhanced infection.

Another theoretical risk is that antibody administration to those exposed to SARS-CoV-2 may avoid disease but modify the immune response such that those individuals mount attenuated immune responses, which would leave them vulnerable to subsequent re-infection. In this regard, passive antibody administration before vaccination with respiratory syncytial virus was reported to attenuate humoral but not cellular immunity. This concern could be investigated as part of a clinical trial by measuring immune responses in those exposed and treated with convalescent plasma to prevent disease. If the concern proved real, these individuals could be vaccinated against COVID-19 when a vaccine becomes available. *These concerns seem modest compared to the possibility of limiting the duration and severity of disease, and avoiding interventions like mechanical ventilation, ARDS and sepsis.*

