### **3.3 Exploratory Endpoints**

- Symptom inventory

These endpoints will determine the ability of CP to increase the titers of neutralizing antibodies in recipients.

- Antibody titers at pre-infusion, post-infusion and at 15 and 30 days in CP recipients and controls
- Spike protein IgG antibody titers pre and post CP administration

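### Section 8.1.3 reads a rise in spike titers as showing that CP leaves the recipient's own response unimpaired; a weakened response would also rise, and no section specifies the between-arm comparison that could show it

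*Combined protocol and SAP*

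**What the plan says.** The relevant bullet in section 8.1.3 has two parts. The first sets the measurement and its general purpose: "Assessment of S1 titers in CP recipients and controls pre-CP, 1 hr post, 15 and 30 days post to assess the impact of CP". The second adds an aim and its interpretation: to "determine whether titers rise with time (showing endogenous response not negatively impacted by CP"). The bullet does not say from which sample a rise is counted, or in which arm.

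Earlier in the same section there is a softer statement confined to the treated arm: "Increase in antibodies over time in CP recipients, if it occurs, will also inform about development of innate immunity after passive immunization".

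Section 3.3 lists the endpoint for both arms: "Antibody titers at pre-infusion, post-infusion and at 15 and 30 days in CP recipients and controls". Section 1.1 classes titers as secondary, sections 1.2 and 3.3 class them as exploratory, and the heading of 8.1.3 says secondary.

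The background to the interpretation is section 2.3.1, which names as a theoretical risk that antibody given to exposed people may "modify the immune response such that those individuals mount attenuated immune responses, which would leave them vulnerable to subsequent re-infection". It adds: "This concern could be investigated as part of a clinical trial by measuring immune responses in those exposed and treated with convalescent plasma".

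**The concern.** The risk in section 2.3.1 is a reduced response, not an absent one. Sections 1.2 and 5.1 restrict entry to a first episode with at most 7 days of symptoms at randomization. At that stage antibody is expected to climb over the next two to four weeks whatever the treatment. A rise is therefore what one would see with no attenuation, with moderate attenuation, and in most cases with severe attenuation. It does not separate these possibilities, yet it is the only observation that 8.1.3 links to a conclusion about impairment.

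Characterizing the immunologic response to CP is the trial's stated secondary objective. If the parenthesis were carried into the report, the trial would very probably state that the recipient's own response was unaffected, whether or not that was true.

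**Working it through.** **1. The plan's own figure.** Section 2.2 dilutes one unit of about 250 ml into about 15 L: 15,000/250 = 60, which matches its stated 60-fold. With the current unit of about 200 ml (section 6.1.2) it is 15,000/200 = 75. Donor antibody therefore adds little: a 1:160 unit adds a reciprocal titer of 160/75 = 2.1 (160/60 = 2.7), and a 1:2560 unit adds 2560/75 = 34 (2560/60 = 43).

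**2. Simplest illustration.** The documents give no recipient titers, so these are assumptions: baseline 20, control Day 30 value 640. Fold rise = 640 × (1 − attenuation)/20.
- No attenuation: 640/20 = 32-fold.
- 50%: 320/20 = 16-fold.
- 90%: 64/20 = 3.2-fold.

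Titers rise in every case.

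**3. Allowing for donor antibody, counting the rise from the 1-hour sample.** Let B be the baseline titer, C the control Day 30 titer, D the donor titer and a the attenuation of the recipient's own increase. Assume a donor-antibody half-life of 21 days, full distribution by 1 hour, and that the dilution figure applies to S1 titers.
- 1 hour: B + D/75.
- Day 30: B + (1 − a)(C − B) + (D/75) × 2^(−30/21), where the last factor is 0.37.

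With B = 20, C = 640, D = 640, the 1-hour value is 20 + 8.5 = 28.5. At a = 50%, Day 30 is 20 + 310 + 3.2 = 333.2, an 11.7-fold rise. The rise is 22.5-fold with no attenuation, 6.2-fold at 75% and 3.0-fold at 90%.

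Over the grid B = 5, 20, 80; C = 160, 640, 2560; D = 160, 640, 2560 (27 combinations), titers rose in:

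| Attenuation | Combinations with a rise |
|---|---|
| 50% | 27/27 |
| 75% | 26/27 |
| 90% | 24/27 |

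Every exception had C = 160 and D = 2560. Section 6.2 allows labels above 1:10240, which the grid does not cover. With D = 10240, B = 20, C = 640 and a = 90%, the 1-hour value is 20 + 136.5 = 156.5 and Day 30 is 20 + 62 + 50.7 = 132.7. That is no rise from 1 hour, but still 132.7/20 = 6.6-fold from the pre-infusion sample.

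**4. What a between-arm contrast would show.** A halving is 1 log2 unit. Per-arm n for 80% power, two-sided 0.05, is 2 × (1.960 + 0.842)² × SD². For assumed SDs of 1.5, 2 and 3 log2 units this gives 36, 63 and 142. At 300 per arm (two-thirds of the maximum 450), power is above 0.99, above 0.99 and 0.98.

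The 95% interval factor for the geometric mean ratio is 10^(1.96 × SD × √(2/n)). SD 0.5 log10 with n = 400 gives 1.17; SD 0.9 with n = 300 gives 1.39. Around a ratio of 0.5, even the wider interval runs from 0.5/1.39 = 0.36 to 0.5 × 1.39 = 0.70, well short of 1.

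**5. Whether another section supplies that contrast.**
- Section 9.2.4 gives means, standard deviations and confidence intervals for continuous secondary endpoints, with no comparison of titers between arms.
- The table in section 3 justifies the titer endpoints by whether CP raises recipient titers and how donor antibody distributes. It does not mention attenuation.
- Section 9.2.1 uses pre-treatment antibody only as a possible modifier of the clinical effect.
- The pseudovirus assay in 8.1.3 covers CP recipients only, before and after infusion.

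No section compares the arms at Day 15 or Day 30.

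**The case against.** The best defence is the full sentence. It covers recipients and controls and speaks of assessing the impact of CP, which is naturally read as a comparison. This stands as far as the data go. A reader might infer that the trial cannot detect attenuation; the documents do not support that, because controls are sampled at the same times and step 4 shows that the contrast would be informative. What remains is that the comparison is never stated, while the inference from a rise is.

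A reader might also take the parenthesis for a formal decision rule. It is not: it is a gloss in a list of assays, with no threshold, test or consequence.

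Nor do the documents support the idea that the rise could be mainly donor antibody. Section 2.2 does say that "the protection conferred by the transferred immunoglobulin can last from weeks to months", but this concerns protection, and the same paragraph gives the 60-fold dilution. The 1-hour sample also captures most of the passive step. Donor antibody is a caveat here, not the main argument.

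Finally, section 2.3.1 calls the risk theoretical and the concern modest, and frames it mainly around exposed people who avoid disease, whereas this trial enrols symptomatic patients. Section 8.1.3 does not present itself as the check on that risk. This lowers the stakes but does not make the inference valid.

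**Conclusion.** The inference in section 8.1.3 is invalid and should be removed. Under assumed titers, attenuation of 50% leaves a 16-fold rise and 90% a 3.2-fold rise. With dilution and decay of donor antibody modelled, a rise persists in 24 of 27 assumed combinations even at 90%. A rise can fail to appear under severe attenuation combined with high-titer plasma, so the criterion is weak rather than wholly uninformative.

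The defect lies in the stated interpretation and the missing contrast, not in design or sampling. Titer levels, standard deviations and half-life are assumptions. The qualitative conclusion needs only that control titers rise substantially after enrollment.

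A reader might infer that the trial's safety conclusions are compromised. They are not: adverse-event review and the DSMB do not depend on this endpoint, and neither do the primary analysis or the stopping rules.

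**What to change.** In section 8.1.3, delete the parenthetical inference. State that any conclusion about attenuation rests on the CP/control geometric mean titer ratio at Day 15 and at Day 30, with 95% interval, adjusted for pre-infusion titer. Report it as an estimate; a margin is not essential for an endpoint classed partly as exploratory.

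Add two notes:
- Flag samples taken after non-study CP, which sections 1.5 and 6.4 permit on hospitalization, or after vaccination during follow-up. Show the ratio with and without them.
- State that residual donor antibody may raise CP-arm titers, so a ratio near 1 does not by itself exclude attenuation. Under the assumptions above, a 1:2560 unit leaves 34 × 0.37 = 12.7 at Day 30. That is 2% of a control titer of 640 and 8% of one of 160, so the caveat matters most for low responders and very high-titer units.

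The cost is a wording change and one added analysis of samples already planned in both arms. The downside is a less favourable interpretive claim.

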### **8.1.4 Blood Sample Storage, Processing and Shipping for Antibody Titer Testing**

Each site will ship the 4 blood samples from each participant to the central testing laboratory (University of Pittsburgh). The site can ship all of the samples for one participant together in a single package. Labels for samples with barcodes will be provided to sites in advance in order to ensure accurate sample tracking. Labeling samples with the subject ID from WebDCU can serve as a backup procedure.

*Antibody titres:* To determine the immunologic response to CP administration, we will measure anti-SARS-CoV-2 IgG, IgM and neutralizing antibody titres pre-intervention, post-intervention and at days 15 and 30.

Testing will be identical to the testing performed to determine the titer of the donor CP. We will determine the IgG/IgM titers to SARS CoV-2 S (Spike) protein using enzyme linked immunoassays (BSL-2+). There are multiple assays available and in development. We will compare titres from the Vitalant (Ortho VITROS Anti-SARS-CoV2 Total) assay to titres from other assays (e.g. Euroimmun ELISA) whenever possible to determine the concordance. In a subset of these samples, we will measure antibody neutralization titers using the gold standard assay, a viral plaque assay performed in a BSL-3 facility at University of Pittsburgh. This will allow us to determine whether high titers in binding assays actually represent superior neutralization capacity for inhibiting SARS-CoV-2 infection.

### **8.1.5 Assessment of Blinding**

As part of follow-up assessments on Days 2 and 15, investigators will ask subjects to indicate which intervention (CP or placebo) they believe that they received, and how confident they are in their response. If blinding is successful, subjects will be no more accurate than chance. We will also examine the rate of successful follow-up contacts between groups. If blinding is successful, missingness will not differ between groups. We will have local site investigators review emergency department practice and communication, potentially to create a corrective action plan, in the event we see a pattern at a site that suggests a high rate of subject unblinding.

If the subject becomes knowledgeable of their treatment assignment at any point during study participation, this will be documented in the study database. Regardless of unblinding, the subject will remain in the study and be part of the analysis population.

### **8.1.6 Clinical and Demographic Data**

At enrollment, we will collect data from the subject and the medical record to validate eligibility for enrollment into the trial and to assess risk factors for developing severe/critical COVID-19 illness. This data includes but is not limited to: inclusion and exclusion criteria, demographic information, vital signs, medical history, and medications. We will collect time of COVID-19 symptom onset by self-report from the subject.

## 8.2 Safety and Other Assessments

### 8.2.1 Safety Assessment

All adverse events (AEs) will be recorded until ED discharge. All AEs occurring until discharge from the emergency department must be reported in WebDCU™. After discharge from the emergency department and at each follow-up contact until the end of study, only serious adverse events will be reported in WebDCU and any event that leads to hospitalization or an ED or urgent care visit even if deemed non-serious. Investigators will also review medical records on Day 30 for any serious adverse events.

Subjects will be monitored for the following plasma-specific AEs:

- Transfusion reactions: fever, rash, itching
- Serious allergic reactions (anaphylaxis or bronchospasm requiring treatment)
- Transfusion Associated Acute Lung Injury (TRALI), as defined by <https://www.ncbi.nlm.nih.gov/pmc/articles/PMC6850655/> (21). Given that these are patients with other risk factors for ARDS, a diagnosis of "possible TRALI" will require stable respiratory status in the 12 hours before transfusion. Because TRALI may mimic the natural progression of COVID-19, the demonstration of HLA antibodies in the donor product that matches the recipient's HLA type will also be necessary to make the diagnosis of "possible TRALI".
- Transfusion Associated Circulatory Overload (TACO)

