Finally, there are risks associated with any transfusion of plasma including transmission of transfusion transmitted viruses (e.g. HIV, HBV, HCV, etc.), allergic transfusion reactions, anaphylaxis to transfusion, febrile transfusion reaction, transfusion related acute lung injury (TRALI), transfusion associated cardiac overload (TACO), and hemolysis should ABO incompatible plasma be administered. In addition, donors will fulfill donor requirements for whole blood donation and frequent apheresis plasma donation with the exception of recent illness, in this case COVID-19 infection. With current practice, transfusion transmission of infections is very rare. In addition, the risk of TRALI is also very rare because CP will be collected from populations with reduced risk for allo-antibodies such as: males, never pregnant females, and females who test negative for HLA antibodies.

Preliminary safety results from the Expanded Access Program for CP in moderate-severe COVID-19 have been posted, but not yet peer-reviewed (<https://www.medrxiv.org/content/10.1101/2020.05.12.20099879v1>). Among 5000 transfusions, there were 36 serious adverse events (0.7%) with 25 adjudicated as related (0.5%). Related

events included mortality (n=4, 0.08%), TACO (n=11, 0.22%), TRALI (n=7, 0.14%) and allergic reaction (n=3, 0.06%). Another 11 deaths were reported but judged not to be related.

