## 6.2 Preparation/Handling/Storage/Accountability

NHLBI is collaborating with BARDA who will contract with Vitalant to provide up to 500 units of CP with known titers of neutralizing SARS-CoV2 antibodies of 1:160 or higher for this trial. The supplier (Vitalant) has already collected many units of CP. Donors will meet current FDA eligibility requirements for COVID-19 Convalescent Plasma (<https://www.fda.gov/vaccines-blood-biologics/investigational-new-drug-ind-or-device-exemption-ide-process-cber/recommendations-investigational-covid-19-convalescent-plasma>)

1. COVID-19 convalescent plasma will be collected from individuals who meet all donor eligibility requirements.
2. COVID-19 convalescent plasma is collected from individuals who meet all of the following qualifications:
  - a. A positive serological test for SARS-CoV-2 antibodies after recovery.
  - b. Complete resolution of symptoms at least 14 days before the donation. A negative result for COVID-19 by a diagnostic test is not necessary to qualify the donor.
  - c. Male donors, or female donors who have not been pregnant, or female donors who have been tested since their most recent pregnancy and results interpreted as negative for HLA antibodies.

Serologic testing will be performed using state-of-the-art research methods. Specifically, CP will be tested using a chemiluminescent test for IgG and IgM against spike protein (Ortho VITROS Anti-SARS-CoV2 Total) or equivalent assay. This assay has been granted FDA Emergency Use Authorization (EUA). If this qualitative test is positive, then the CP is also tested with the Vitalant Research Institute SARS-CoV2 Reporter Viral Particle Neutralization (RVPN) test or equivalent assay. The presence of antibodies are generally confirmed within 48 hours of donor collection. Assays will be conducted by a central laboratory and assays will also be made available to

study investigators. The CP is labeled with the titer from the RVPN test as: negative, <1:40, positive 1:40, 1:160; 1:640, 1:2560, 1:10240, >1:10240. We do not intend to use CP with 1:40 or <1:40 titer.

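### A case can be called possible TRALI only with a donor-recipient HLA match that no planned test supplies, so a zero count would be weak evidence of safety

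*Combined protocol and SAP*

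**What the plan says.** Section 8.2.1 lists four plasma-specific events to be monitored. The lung-injury item reads "Transfusion Associated Acute Lung Injury (TRALI), as defined by", followed by a link to a published definition. Because trial participants have other risk factors for ARDS, the section adds two conditions for the diagnosis of possible TRALI. The first is 12 hours of stable respiratory status before transfusion. The second is immunological: "the demonstration of HLA antibodies in the donor product that matches the recipient's HLA type will also be necessary". That sentence opens with its reason, that TRALI can look like progression of COVID-19: "Because TRALI may mimic the natural progression of COVID-19, the demonstration of HLA antibodies in the donor product".

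Two other sections describe who donates. Section 6.2 accepts male donors, never-pregnant female donors, and "female donors who have been tested since their most recent pregnancy and results interpreted as negative for HLA antibodies". Section 2.3.1 draws the inference that "the risk of TRALI is also very rare because CP will be collected from populations with reduced risk for allo-antibodies".

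Section 2.3.1 also gives the only TRALI rate in the documents: 7 cases (0.14%) among 5000 transfusions in an expanded access program for moderate-severe COVID-19.

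**The concern.** The label depends on two laboratory facts: an HLA antibody in the unit, and the recipient's HLA type. If neither is measured, a participant with typical acute lung injury after plasma cannot be classified as possible TRALI, however convincing the clinical picture. Donor selection also makes a positive antibody result less likely when a test is done.

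Safety is part of the primary objective (Section 1.2). With an event this rare, one case is the difference between reporting that TRALI was observed and reporting that there was none. A reader of the final report could take zero as reassurance without knowing whether the required tests were ever run.

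**Working it through.** **Step 1. Look for the HLA data in the plan.**
- Section 1.4 (schedule) and Section 1.5.1.3 (day 0): ABO or blood type, and research blood draws for antibody titers. No HLA typing.
- Section 6.2: units are tested for SARS-CoV-2 antibodies, and a sample of each unit goes to the core laboratory for antibody characterization, described as SARS-CoV-2 assays. HLA-antibody testing appears only as a qualification for previously pregnant donors.
- Sections 8.1.3 and 8.1.4: recipient blood is stored as serum and plasma and tested for SARS-CoV-2 antibodies. The optional extra whole blood is for a study of the adaptive immune response. No HLA assay is named.
- Section 8.3.5: narratives of serious events include additional test results if any were done. This permits an HLA work-up but does not require one.

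So no planned test supplies either fact. An event-triggered work-up could, but the documents do not say who would do it or on which sample.

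**Step 2. Reproduce the stated rate.** 7/5000 = 0.0014 = 0.14%, as stated. The exact (Clopper-Pearson) 95% interval runs from the 0.025 quantile of Beta(7, 4994) to the 0.975 quantile of Beta(8, 4993): 0.056% to 0.288%. Applying this rate to outpatients is an assumption.

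**Step 3. Expected count without the HLA condition.** With n plasma recipients and rate p, the expected count is n × p and P(0) = (1 − p)^n.
- n = 450 (revised maximum): 450 × 0.0014 = 0.63; P(0) = 0.9986^450 = 0.532. Over the interval, 0.25 to 1.30 cases are expected.
- n = 300 (original maximum): 300 × 0.0014 = 0.42; P(0) = 0.657.

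**Step 4. Add the HLA condition.** Let s be the share of cases that could show a match. The documents do not give it, so it is varied. Then P(0) = (1 − s × p)^n, with n = 450:

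| s | Expected at 0.14% | P(0) at 0.14% | P(0) at 0.056% | P(0) at 0.288% |
|---|---|---|---|---|
| 1 (no condition) | 0.63 | 0.532 | 0.776 | 0.273 |
| 0.5 | 0.32 | 0.730 | 0.881 | 0.523 |
| 0.25 | 0.16 | 0.854 | 0.939 | 0.723 |
| 0.1 | 0.06 | 0.939 | 0.975 | 0.878 |
| 0 (no HLA test done) | 0 | 1 | 1 | 1 |

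**Step 5. What a zero would then say.** The one-sided 95% upper bound for 0/450 is 1 − 0.05^(1/450) = 0.66%. In the last row of the table this bound would come out whatever the true rate. The plan does not call for such a bound; it is shown only to illustrate how little a zero count would mean.

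**The case against.** The strongest reply is that little is lost, because the event is captured and can be attributed to plasma without the label. Most of this stands. Under Section 8.2.1 all adverse events are recorded until ED discharge. After that, serious events and any event leading to hospital, ED or urgent care are reported. Under Section 8.3.4 a reasonable possibility of relatedness needs two of three conditions, and a suitable time relationship plus a known pattern of response is enough. No HLA result enters that grading. The independent medical safety monitor has transfusion expertise (Section 10.2), and nothing makes the review wait for HLA data.

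Three stronger readings are tempting, and the documents support none of them.
- *The count is near zero by construction, or the criterion cannot be met.* Unit samples reach the core laboratory, triggered tests are allowed, and male and never-pregnant donors are at reduced risk but not shown to be antibody-negative. Rarity alone makes zero slightly more likely than not at 0.14%, and donor selection also lowers the true risk, so part of a low count would be real.
- *The whole TRALI outcome is disabled.* The extra conditions are written for possible TRALI. The natural reading directs this population there, but the cited definition is not available to check how the categories relate.
- *Cases would be lost or put down to COVID-19.* The reporting and relatedness rules above do not force that.

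It is also fair that a rare-event work-up may sit in the Manual of Procedures, which is not available here, and that the wish for a specific definition is legitimate. What the reply leaves unanswered is the label itself: the rule makes it depend on data the plan does not collect and says nothing about a suspected case with no HLA result.

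**Conclusion.** The concern holds for the possible TRALI label. Applied to the data the plan collects, the rule withholds that label from a clinically typical case unless an unplanned HLA work-up is done. The count is therefore weak evidence of safety, although the event would still be reported and could be graded as related.

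The size is modest. At the assumed 0.14%, the HLA condition moves the probability of a zero count in 450 recipients from 53% to between 73% and 94%, and to 100% with no HLA testing. These figures rest on carrying a moderate-severe rate over to outpatients and on an assumed share of 50% to 10% of cases able to show a match. The absence of any named HLA test rests on neither assumption. The change is worth making because it preserves the meaning of a named safety outcome at little cost.

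**What to change.** Reconcile Sections 6.2, 8.1.3, 8.1.4, 8.2.1 and 8.3.5. State who would perform HLA-antibody testing of the unit and HLA typing of the recipient, on which sample, and how a suspected case with no HLA result is classified and reported.

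In the safety tables, report by arm:
- all acute respiratory events after infusion that meet the clinical part of the cited definition and the 12-hour stability condition, whatever the HLA result;
- HLA-confirmed cases, as a subset;
- the number of such events with no HLA result.

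Section 9.2 currently specifies no by-arm table of this kind. The cost is protocol and table wording. It uses events already collected, requires no new test, and keeps the specific definition as a subset. The downside is that some COVID-19 progression will be counted in both arms. The saline arm shows how much, within the limits of small numbers and of ED staff who know the allocation (Section 4.2).
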